#### **7.1.7 Withdrawal From the Study Due to Severe Flares**

A patient will be withdrawn from the study for a severe lupus flare as per the SFI as described in section 3.6.

#### **7.1.8 Medical Emergencies**

Medical emergencies must be reported to the individual identified in the clinical study personnel contact information section of this protocol.

Equipment, supplies, and properly skilled medical personnel must be accessible for an adverse event requiring immediate treatment. Any dose of study drug (whether the investigational product, reference therapy, or a placebo), whether taken intentionally or unintentionally, in excess of that prescribed must be immediately reported to ImmuPharma or its designee. When the identification of the study drug must be known, the investigator must follow the procedures outlined in section 3.8.

#### **7.1.9 Protocol Deviations Because of an Adverse Event**

If a patient experiences an adverse event or medical emergency, departures from the protocol may be allowed on a case-by-case basis. After stabilization and/or treatment for the emergency to protect patient safety has been administered, the investigator or other physician in attendance in such an emergency must contact the individual identified in the clinical study personnel

contact information section of this protocol, as soon as possible to discuss the circumstances of the emergency. The investigator, in consultation with ImmuPharma or its designee, will decide whether the patient should continue to participate in the study. Any protocol deviation related to adverse events must be noted on the CRF and in source documents along with the reason for such deviations.

## **7.2 Clinical Laboratory Tests**

All clinical laboratory test results outside of the reference range will be interpreted by the investigator using the following categories:

- abnormal but not a clinically significant worsening
- abnormal and a clinically significant worsening

A laboratory test result that has significantly worsened (according to medical judgment) compared with the baseline result will be recorded on the CRF as an adverse event and monitored as described in section 7.1.2. An adverse event includes a laboratory or diagnostic test abnormality (once confirmed by repeat testing) that results in the withdrawal of the patient from the study, the temporary or permanent cessation of treatment with study drug, or requires medical treatment or further diagnostic work-up.

Clinical laboratory tests (serum chemistry, hematology, and urinalysis) will be performed at screening (visit 1), baseline/start of study drug treatment (visit 2), visits 4 through 15, and at the final assessment (or early termination). Clinical laboratory tests will be performed using the central laboratory identified in the front matter of this protocol (and in the Laboratory Procedures Manual provided in the study file documents). Specific laboratory tests to be performed are listed below.

### **7.2.1 Serum Chemistry**

The following serum chemistry tests will be performed:

- calcium
- phosphate
- sodium
- potassium
- chloride
- bicarbonate or carbon dioxide
- glucose
- blood urea nitrogen (BUN)
- creatinine
- cholesterol
- uric acid
- ALT
- AST
- lactate dehydrogenase (LDH)

- gamma-glutamyl transpeptidase (GGT)
- alkaline phosphatase
- creatine phosphokinase
- total protein
- albumin
- total bilirubin
- direct bilirubin

### **7.2.2 Hematology**

The following hematology tests will be performed:

- hemoglobin
- hematocrit
- platelet count
- absolute neutrophil count (ANC)
- white blood cell (WBC) count and differential count
  - polymorphonuclear leukocytes (neutrophils)
  - lymphocytes
  - eosinophils
  - monocytes
  - basophils
  - metamyelocytes

### **7.2.3 Urinalysis**

Urinalysis will include testing for the following:

- protein
- glucose
- ketones
- blood (hemoglobin)
- pH
- specific gravity
- spot protein-creatinine ratio
- creatinine Clearance
- eGRF
- microscopic
  - bacteria
  - red blood cells (RBCs)
  - WBCs

- Casts
- crystals

## **7.2.4 Other Clinical Laboratory Tests**

### **(a) Serology Tests**

Serology tests to be performed at screening will consist of anti-dsDNA, ANA, C3, and C4. Serology tests to be performed at each subsequent visit (visit 2 [week 0; baseline/start of study drug treatment] through visit 16 [week 52], excluding visit 3 [week 2]) will consist of anti-dsDNA Ab, C3, and C4. In addition, the following serology tests will be performed at visit 2 (week 0; baseline/start of study drug treatment), visit 4 (week 4), visit 6 (week 12), visit 9 (week 24), visit 12 (week 36), and the final assessment (or early termination) (visit 16 [week 52]): anti-U1-70K snRNP Ab, ANA, anti-Sm Ab, and CRP, IgG, IgM, IgA and IgE.

### **(b) Hemolysis Testing**

A Coombs' test will be obtained at screening. At subsequent visits, if hemolysis is suspected or confirmed, Coombs' test, haptoglobin, and a peripheral smear will be obtained.

### **(c) Other Tests**

Other clinical laboratory tests will be performed to ensure the safety of the patients, but will not be an assessment of the safety of the study drug.

At screening (visit 1), patients will have serology A tests for HBsAg and HCV Ab. A urine pregnancy test will be performed for all women, regardless of childbearing potential, at screening (visit 1), baseline (visit 2 [week 0]), visits 4 through 15 (weeks 4 through 48), and the final assessment (or early termination) (visit 16 [week 52]). Any patient becoming pregnant during the study will be withdrawn. All pregnancies that occur during the study, or within 14 days of completion of the study, are to be reported immediately to the individual identified in the clinical study personnel contact information section of this protocol, and the investigator must provide ImmuPharma or its designee, by facsimile, with a signed pregnancy tracking form. The facsimile to the sponsor is to be addressed as follows: to be determined. All patients who become pregnant will be monitored to the completion or termination of the pregnancy. If the pregnancy continues to term, the outcome (health of the infant up to 8 weeks of age) will be reported to the sponsor. Any complication of pregnancy will be reported as an adverse event or serious adverse event, as appropriate.

## **7.3 Vital Signs**

Vital signs will be measured at all study visits. Vital signs include the following:

- pulse
- seated blood pressure (systolic and diastolic)
- temperature

Before pulse and blood pressure are measured, the patient must be in a seated position and resting for at least 5 minutes. (The same position and arm should be used each time vital signs

are measured for a given patient.) Any vital sign value that is judged by the investigator as a clinically significant change (worsening) compared to a baseline value will be considered an adverse event, recorded on the CRF, and monitored as described in section 7.1.2.

#### **7.4 Electrocardiography**

A 12-lead ECG will be conducted at screening (visit 1) and at the final assessment (or early termination). A qualified physician will be responsible for providing interpretation of the ECG. Any ECG finding that is judged by the investigator as a clinically significant change (worsening) compared to a baseline value will be considered an adverse event, recorded on the CRF, and monitored as described in section 7.1.2.

#### **7.5 Physical Examinations**

Physical examinations (including height to be obtained at the screening visit only) will be performed at screening (visit 1) and at the final assessment (or early termination). Symptom directed physical examination evaluations and the 28-joint count examination for pain and tenderness will be performed at baseline/start of study drug treatment (visit 2) and visits 4 through 16. Body weight will be recorded during all physical examinations. Physical examination findings will be classified using standard categories as listed on the CRFs. Any physical examination finding that is judged by the investigator as a clinically significant change (worsening) compared to a baseline value will be considered an adverse event, recorded on the CRF, and monitored as described in section 7.1.2.

#### **7.6 Other Safety Measures and Variables**

##### **7.6.1 Concomitant Therapy or Medication**

Concomitant therapy or medication usage will be monitored throughout the study. Details of prohibited medications may be found in section 5.2.

##### **7.6.2 Columbia-Suicide Severity Rating Scale**

An evaluation for suicidality will be administered directly to the patient using IRT. (ERT), at baseline and at each visit during the treatment period using the Columbia-Suicide Severity Rating Scale (C-SSRS). The C-SSRS assesses suicidality from ideation to behaviors and monitors the potential emergence of suicidality in clinical studies. The C-SSRS Baseline version will be performed at baseline (visit 2) and the C-SSRS since Last Visit version will be performed at visits 4 through 16 (or final assessment visit).

If the C-SSRS is positive at any visit during the treatment period, the patient will be evaluated by the investigator to determine if a formal evaluation by a trained mental health professional is indicated. If the patient is determined to be a risk to himself or herself or others, the sponsor will be notified and the patient will be withdrawn from the study.

##### **7.6.3 Anaphylaxis Evaluation**

Anaphylaxis is defined as a serious allergic reaction that is rapid in onset and may cause death ([Sampson et al 2006](#)). Any patient who experiences an adverse event that presents with signs and/or symptoms that are suggestive of an anaphylactic, anaphylactoid, or drug hypersensitivity reaction will be evaluated using the Clinical Criteria for Diagnosing Anaphylaxis. The clinical criteria to be applied for diagnosing anaphylaxis are in [Appendix I](#).

## **7.7 Methods and Timing of Assessing, Recording, and Analyzing Safety Data**

Methods and timing of assessing safety data are discussed in section [3.11](#). Procedures for recording safety data are discussed in section [13.1](#), and methods of analyses are discussed in section [9.7](#).

Furthermore, all adverse events will be reviewed on a periodic basis (eg, scheduled safety reviews for study drug) as interim/preliminary safety databases become available (see section [7](#)).

An independent, external DSMB will oversee the safety of the patients enrolled in the study and monitor the occurrence of flare throughout the study (see section [3.6](#)). This study may be prematurely terminated if, in the opinion of the DSMB or the sponsor, there is sufficient and reasonable cause. Written notification documenting the reason for study termination will be provided by the terminating party to all involved.

## **8 ASSESSMENT OF PHARMACOKINETICS AND IMMUNOGENICITY**

### **8.1 Pharmacokinetic Assessment**

#### **8.1.1 Pharmacokinetic Blood Sampling**

Blood samples (5 mL) for pharmacokinetics will be collected from patients at selected North American and Western European study centers via venipuncture or indwelling catheter prior to and 5 minutes and 1, 2, and 24 hours after study drug administration at weeks 0, 16, and 32 (visits 2, 7, and 11, respectively). A blood sample for measurement of the concentration of IPP-201101 will also be obtained from all patients who have a serious adverse event and/or have an adverse event leading to withdrawal from the study. The actual dates and times of study drug administration and the date and time of sampling will be recorded on the CRF.

#### **8.1.2 Processing, Handling, and Shipping of Samples for Pharmacokinetic Analysis**

Instructions for processing, handling, and shipping blood samples for pharmacokinetic analysis will be provided to the study centers in the laboratory manual provided by ImmuPharma or its designee..

### **8.2 Immunogenicity**

Anti-IPP-201101 Ab testing will be performed at visit 2 (week 0; baseline/start of study drug treatment), visit 3 (week 2), visit 4 (week 4), visit 6 (week 12), visit 8 (week 20), visit 10 (week 28), visit 12 (week 36), visit 14 (week 44), and the final assessment (or early termination) (visit 16 [week 52]). All samples will be collected prior to administration of study drug at that particular visit.

Any patient with a positive test result in the confirmatory assay at the final study visit will be followed with additional immunogenicity testing at 8-week intervals until the level returns to baseline value or the levels are judged by the investigator to be chronic, or the patient is lost to follow-up.

### **8.3 Methods and Timing of Pharmacokinetic Blood Sampling and Immunogenicity**

Methods and timing of blood sampling for plasma concentrations of IPP-201101 and presence of anti-IPP-201101 Ab are discussed in section 3.11. Procedures for recording blood sampling for plasma concentrations and detection of anti-IPP-201101 Ab are discussed in section 13.1. Methods for analyses of blood samples for concentrations of IPP-201101 and of anti-IPP-201101 Ab (as noted above in section 8.2) are discussed in section 10.8.

## **9 ASSESSMENT OF IN VITRO INTRACELLULAR AND SECRETED CYTOKINE RESPONSE**

### **9.1 Blood Sampling for in vitro intracellular and secreted cytokine response**

Blood samples (5 mL) for in vitro intracellular and secreted cytokine response will be collected from patients at selected study centers via venipuncture or indwelling catheter prior study drug administration at weeks 0, 4, 24, and 48 (visits 2, 4, 9 and 15, respectively). The actual dates and times of study drug administration and the date and time of sampling will be recorded on the CRF.

### **9.2 Processing, Handling, and Shipping of Samples for in vitro intracellular and secreted cytokine response**

Instructions for processing, handling, and shipping blood samples for in vitro intracellular analysis will be provided to the study centers in the laboratory manual provided by ImmuPharma or its designee.

### **9.3 Methods and Timing of in vitro proliferation and secreted cytokine response**

Methods and timing of blood sampling for in vitro intracellular and secreted cytokine response of IPP-201101 are discussed in section 3.11. Procedures for recording blood sampling are discussed in section 13.1. Methods for analyses of blood samples for in vitro proliferation and secreted cytokine response of IPP-201101 are discussed in section 10.9.

## **10 STATISTICS**

### **10.1 Study Design and Randomization**

This is a Phase 3 randomized, double-blind, parallel-group, placebo-controlled study. Treatment assignment will be stratified for the following 3 baseline characteristics (as described in section 3.3): by region, SLEDAI-2K screening total score (6 to 9 or  $\geq 10$ ), and racial-ethnic group classification (black/Hispanic or others). Within each stratum, eligible patients will be randomly

assigned with a 1:1 ratio to receive either 200 mcg of IPP-201101 or placebo sc every 4 weeks for 48 weeks. Study investigators, patients, and ImmuPharma study staff will be blinded to the treatment assignments during the study.

## **10.2 Sample Size and Power Considerations**

This study is designed to estimate and assess the significance of the difference between a 200-mcg dose of IPP-201101 and placebo in the proportion of SRI responders at week 52. With 100 evaluable patients per group (200 in total), this study will have 90% or greater power to detect a 25% or greater difference in the proportion of SRI responders between the IPP-201101 group and the placebo group or to detect a 20% difference with an 80% power. This projection using the Pearson

Chi-square test (2-sided,  $\alpha=0.05$ ) is based on an anticipated placebo effect at week 52 of 40% to 45%. This range covers the placebo effect reported in the literature ([Navarra et al 2009](#), [van Vollenhoven et al 2010](#), [Wallace et al 2009](#)) and in a Phase 2b, multicenter, randomized, double-blind, placebo-controlled dose-ranging study of IPP-201101 (study IP-004). The difference between placebo and active which is used in the sample size calculation is 25% based on the results of the Phase IIb study (IP-004) with the same formulation (Zimmer et al. ACR 2012)

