**Statistical Considerations:** The primary efficacy variable is the proportion of patients achieving a combined clinical response using the SRI at week 52. With 100 evaluable patients per group (200 total), this study will have a 90% or greater power to detect a 25% or greater difference or a 20% difference with a 80% power in the proportion of SRI responders between the IPP-201101 group and the placebo group. This projection using the Pearson Chi-square test (2-sided, alpha=0.05) is based on an anticipated placebo effect at week 52 of 40% to 45%. This range covers the placebo effect reported in the literature and in a Phase 2b, multicenter, randomized, double-blind, placebo-controlled dose-ranging study of IPP-201101 (study IP-004). The response rate under active is based on the Phase IIb study performed with the mannitol formulation outside the US. This study showed an absolute 25% response of active over placebo increasing to 40% in the interim analysis. Using a 80% or a 90%power leads to a sample size of 100 evaluable patients per group. The efficacy evaluation will be based on the full analysis set that includes all patients who received at least 1 dose of the study drug.. The statistical method to be used for the SRI is the logistic regression model with treatment and stratification factors as main factors. The SRI is linked to the model factors through the logit function. The likelihood-ratio-based Chi-square statistics will be used for testing the treatment difference between IPP-201101 and placebo in SRI at week 52 at the significance level 0.05. The odds ratio (active/placebo) and associated 95% confidence interval will be determined from the logistic regression model. As sensitivity analyses, the primary analysis will be repeated using another 3 imputation methods to estimate missing SRI at week 52 according to the reason for withdrawal. In the 1st method, patients who withdraw because of lack of efficacy will be classified as treatment failures assessed by SRI at week 52. For patients who withdraw

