### **1.3.2.3 Efficacy and Safety Results From a Completed Phase 2b Study in Patients With Active Systemic Lupus Erythematosus**

The Phase 2b study (study IP-004) was a multicenter, randomized, double-blind, placebo-controlled, dose-ranging study conducted in Bulgaria, Romania, Spain, and Argentina to evaluate the efficacy and safety of treatment with IPP-201101 in patients with active SLE. Patients were randomly assigned to 1 of 3 treatment groups, as follows:

- (1) 200 mcg of IPP-201101 sc every 4 weeks (3 sc injections at baseline and weeks 4 and 8; total dose of 600 mcg) and 3 sc injections of matching placebo at weeks 2, 6, and 10, plus standard of care (SOC)
- (2) 200 mcg of IPP-201101 sc every 2 weeks (6 sc injections at baseline and weeks 2, 4, 6, 8, and 10; total dose of 1200 mcg) plus SOC
- (3) placebo sc every 2 weeks (6 sc injections at baseline and weeks 2, 4, 6, 8, and 10) plus SOC

A total of 204 patients were planned to be enrolled in this study. The primary efficacy variable for the study was the SLE responder index (SRI) at week 12. The SRI was defined as a reduction from baseline in the SLEDAI 2000 (SLEDAI-2K) total score of at least 4 points, no worsening in Physician's Global Assessment (PhGA) (with worsening defined as an increase in PhGA of more than 0.30 point from baseline), no new British Isles Lupus Assessment Group A (BILAG A) body system score, and no more than 1 new BILAG B body system score from baseline. Statistical significance was assessed at  $\alpha=0.025$ . Two interim analyses were conducted. The 1st interim analysis was conducted and data reviewed in December 2008 when 125 patients enrolled in the study completed 12 weeks of study drug treatment and had at least 1 efficacy measurement. After data from the 1st interim analysis were reviewed, a decision about the future clinical development of IPP-201101 was made, and enrollment of additional patients into the study was stopped. At this time, 150 patients had been enrolled in the study. The 2nd interim analysis was performed in June 2009 when the 125 patients from the 1st interim analysis completed the study (through week 24). At week 12, there was a statistically significant

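### Do the 25-point difference and the 40-45% placebo range in section 10.2 misstate the IP-004 results enough to need a change?

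*Protocol*

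**What the plan says.** Section 10.2 plans 100 evaluable patients per group. It claims at least 90% power for a difference of 25 points or more and 80% power for 20 points, by a two-sided Pearson chi-square test at 0.05. The calculation assumes "an anticipated placebo effect at week 52 of 40% to 45"%. On where the range comes from, the section says "This range covers the placebo effect reported in the literature" and goes on to name IP-004. On the difference, it says that the figure "which is used in the sample size calculation is 25% based on the results of the Phase IIb study (IP-004"), and it cites a conference abstract.

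The synopsis, under Statistical Considerations, repeats the placebo claim ("This range covers the placebo effect reported in the literature and in a Phase 2b, multicenter") and adds "This study showed an absolute 25% response of active over placebo increasing to 40% in the interim analysis".

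Section 1.3.2.3 reports IP-004 itself. The every-4-weeks arm received "3 sc injections at baseline and weeks 4 and 8; total dose of 600 mcg". The first interim analysis came "when 125 patients enrolled in the study completed 12 weeks of study drug treatment", and the second when the patients from the 1st "interim analysis completed the study (through week 24"). Final SRI rates, every-4-weeks arm against placebo, are:

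- week 12, all patients: 53.1% and 36.2%
- week 12, clinical SLEDAI-2K score of at least 6: 61.9% and 38.6%
- week 24, same subgroup: 69.0% and 56.5%

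For an interim week-12 comparison the section gives p=0.012 but no rates.

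**The concern.** The two sourcing statements can be checked against the protocol's own background section, and on a first reading both fail. None of the three IP-004 placebo rates lies between 40% and 45%: two fall below and one above. The results run only to week 24, so IP-004 has no week-52 placebo rate to compare. The final differences are 16.9, 23.3 and 12.5 points, none of them 25, and the section does not say which analysis set, population or visit the 25 points came from. The 40-point interim figure in the synopsis appears nowhere else.

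If the planning difference had been inflated, the trial would be underpowered. At 100 per group, the all-patient week-12 result would give about 67% power, well short of the 90% a reader of section 10.2 would expect.

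**Working it through.** **Power formula.** Two proportions, 1:1 allocation, pooled variance under the null, two-sided 0.05. With placebo rate a, active rate b, mean m = (a+b)/2 and n = 100 per group:

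s0 = √[2m(1−m)/n], s1 = √[(a(1−a)+b(1−b))/n], power = Φ[((b−a) − 1.96·s0)/s1].

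**1. The plan's own figures.** For 40% against 65%: s0 = 0.0706, s1 = 0.0684, (0.25 − 1.96×0.0706)/0.0684 = 1.63, power 94.9%. In the same way:

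| Placebo | Active | Difference | Power | n per group |
|---|---|---|---|---|
| 40% | 65% | 25 | 94.9% | 82 for 90% |
| 45% | 70% | 25 | 95.3% | 81 for 90% |
| 40% | 60% | 20 | 81.2% | 97 for 80% |
| 45% | 65% | 20 | 81.6% | 96 for 80% |

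Both stated power figures are right, and 100 per group meets both.

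**2. Power at the IP-004 rates shown.**

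| IP-004 result | Difference | Power at 100 per group |
|---|---|---|
| Week 12, all patients, 36.2% and 53.1% | 16.9 | 67.4% |
| Week 12, clinical SLEDAI-2K ≥6, 38.6% and 61.9% | 23.3 | 91.5% |
| Week 24, same subgroup, 56.5% and 69.0% | 12.5 | 44.7% |

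The middle row is the closest match, because inclusion criterion (e) in section 4.1 requires a clinical SLEDAI-2K score of at least 6. The first row includes patients whom this trial excludes. The last row was measured 16 weeks after the last active dose (week 24 minus week 8), whereas this trial doses to week 48 and assesses at week 52.

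**3. Does the placebo range matter?** Put the placebo rate at each IP-004 value instead of 40-45%:

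| Placebo | Power, 20 points | Power, 25 points |
|---|---|---|
| 36.2% | 81.5% | 94.8% |
| 38.6% | 81.3% | 94.8% |
| 56.5% | 85.6% | 97.4% |

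Power never falls below the stated 80% and 90%.

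**4. Is 25 points consistent with IP-004?** First, establish which convention the printed p-values follow. Counts inferred from the percentages, with a pooled two-proportion z test, give:

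| Inferred counts | One-sided p | Two-sided p | Printed |
|---|---|---|---|
| 26/49 and 17/47 | 0.048 | 0.096 | 0.048 |
| 26/42 and 17/44 | 0.0155 | 0.031 | 0.016 |
| 26/49 and 18/47 | 0.073 | 0.147 | 0.073 |
| 29/42 and 26/46 | 0.113 | 0.225 | at least 0.113 |

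For the first row: difference 0.1689, pooled rate 43/96 = 0.448, standard error 0.1015, z = 1.66. The printed values are one-sided.

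Now take the interim p=0.012 as one-sided, so z = 2.257. About 42 per arm follows from 125/3. Solving d = 2.257·√[2m(1−m)/42] at a placebo rate of 36% gives d = 24.6 points. Over 38 to 44 per arm and placebo rates of 30% to 45% (both assumed), d runs from 23.7 to 25.9 points. Read as two-sided, it would be 26.4 to 28.8. A week-12 interim result of about 25 points is therefore implied by section 1.3.2.3 itself.

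The entry-matched subgroup is also about one patient away. One more active responder gives 27/42 − 17/44 = 64.3% − 38.6%, about 25.6 points. One more placebo responder gives 18/44 = 40.9%, inside the range.

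**5. The 40-point interim figure.** With 42 per arm and placebo rates of 30% to 45%, a 40-point difference would give a one-sided p of 0.00006 to 0.00012, far from 0.012. The two cannot describe the same comparison. But there were two interim analyses, and the synopsis gives no population or visit for the 40%, so it cannot be tied to this p-value.

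**The case for a change.** The strongest case for a change is that the protocol itself makes these statements, in two places, so they cannot be left to a statistical analysis plan. Depending on which IP-004 result is meant, power at 100 per group runs from 45% to 95%. The 25 points looks like an early result that shrank to 16.9 in the final all-patient analysis, and an ethics committee or regulator told only that it rests on IP-004 would not see that.

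Part of this stands. As regards IP-004, the claim about the placebo range does not fit the rates shown. The 40% has no support in the visible text. Naming the analysis behind the 25% would have been better practice.

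The rest does not carry. The low end of the power span comes from a population this trial does not enrol and from a visit long after dosing stopped. The protocol also gives a more cautious case of its own: 20 points at 80% power lies below the 23.3 points seen in the matching subgroup. A source for the 25% is cited, but that abstract is not available here, and part of the text next to section 1.3.2.3 was removed before review. That a figure is absent from what can be seen does not make it wrong. Asking the protocol to print 67% power for the all-patient result would be a preference about presentation.

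**Conclusion.** No change to the plan is needed. The placebo statement is loose wording, and the 25 points is a rounded planning value that agrees with the interim p-value and lies 1.7 points above the entry-matched result (25 − 23.3). At that result power is 91.5%, so the claim of at least 90% survives without the rounding. Using any IP-004 placebo rate shown leaves power at 81% or more for 20 points and about 95% or more for 25. The sample size of 200, the endpoint, the test and the primary analysis would be the same however the sentences were worded.

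This rests on three assumptions: that the interim p=0.012 is one-sided like the other printed p-values, with roughly 38 to 44 patients per arm and a placebo rate of 30% to 45%; that the counts inferred from the percentages are right; and that the week-12 subgroup is the fairest available guide to a week-52 contrast, which no IP-004 result can confirm directly. The 40% in the synopsis stays unexplained, but no calculation uses it.
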